#### **2.4.2 Prior, concomitant and post therapies**

Prior and concomitant medications will be summarized in separate tables by cohort and treatment group.

Concomitant rescue and other anti-malarial medications will also be summarized by cohort and treatment group.

Note – The only rescue medication considered in this study is Coartem. All other antimalarial drugs are prohibited and if taken then it will be considered as PD. If Coartem is used after discontinuation of study drug due to early treatment failure, late clinical failure or late parasitological failure then it should be considered as rescue medication,. Rescue medication will be captured along with other concomitant medications by the investigators under rescue medication category.

Any patient on KAE609 who does not need rescue medication up to Study Day 28 will be given Coartem as post therapy at the end of the study (Study Day 29) and will be followed as per standard medical care. Prior medications are defined as drugs taken and stopped prior to first dose of study medication. Any medication given at least once between the day of first dose of study medication and the last day of study visit will be a concomitant medication, including those which were started pre-baseline and continued into the treatment period.

Prior and concomitant medications will be coded according to the latest version of WHO Drug Reference List dictionary which employs the ATC. The number and percentage of patients taking prior and concomitant medications will be summarized for each cohort and treatment by ATC class and preferred term (PT).

Number and percentage of the patients receiving prohibited prior and concomitant drugs will be summarized. Details regarding prohibited drugs are mentioned in [Table 5-9](#). PK related prohibited medications (the drugs which are prohibited only within first 7 days from first dose) and non-PK related prohibited medications will be summarized separately.

Safety set will be used.

### **2.5 Analysis of the primary objective**

The primary objective is to characterize hepatic safety aspects of single and multiple ascending doses of KAE609 in adult malaria patients for treatment of uncomplicated malaria caused by *P. falciparum*.

### **2.5.1 Primary endpoint**

The primary variable is the occurrence of at least 2 CTCAE grades increase from baseline in ALT or AST during the 4 weeks study period.

### **2.5.2 Statistical hypothesis, model, and method of analysis**

The study is a Phase II safety study in African patient population aiming to rule out high incidence of abnormal LFT reported in a couple of earlier studies. As the significance of safety related results is determined by both the frequency of the event and the severity of the event, there is no pre-defined hypothesis. The following analyses will be performed using the SAF set:

- Proportion of patients with occurrence of the primary variable by cohort and treatment group and the 95% confidence interval based on the exact CI (Pearson-Clopper method).
- 2-sided Fisher exact test for each KAE609 treatment group compared to the pooled Coartem.

These results along with patient narratives will be assessed to make decision about whether a KAE609 dosage regimen is safe for further development.

### **2.5.3 Handling of missing values/censoring/discontinuations**

No missing value of the primary variable is expected since the analysis is based on the SAF set and all patients in the SAF set should provide safety observation as they are hospitalized for the first 3 days. No missing data imputation will be done in this study.

### **2.5.4 Supportive analyses**

In the past KAE609 studies, peak LFT occurred during the first 2 weeks after dose administration. For patients who discontinued the study during the first 2 weeks after dose administration, their peak LFT may not be observed. Analyses in [Section 2.5.2](#) will be performed by excluding those patient(s) who discontinued the study before Study Day 15 and did not experience at least 2 CTCAE grades increase from baseline in ALT or AST.

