5.6.3 Premature Study Withdrawal

Patients are considered to be withdrawn prematurely from the study if they do not complete the follow-up visits until Study Day 29.

A patient may voluntarily discontinue participation in this study at any time. The investigator may also, at their discretion, discontinue the patient from participating in this study at any time. Patients may be prematurely discontinued from the study for any of the following reasons:

- Adverse event
- Protocol deviation
- Study closed/terminated
- Loss to follow-up
- Consent withdrawal
- Study or investigator non-compliance
- At the request of the investigator

- Pregnancy

Patients are not obligated to state the reason for withdrawal from this study. However, the reasons for withdrawal, or failure to provide a reason, must be documented by the investigator on the Completion/Withdrawal section of the eCRF.

If a patient is withdrawn from the study for any reason, the investigator must make every effort to perform the study evaluations for Withdrawal visit as specified in the [Table 6-1](#). Withdrawn patients will not be replaced.

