5.6.5 Loss to follow-up

For subjects whose status is unclear because they fail to appear for study visits without stating an intention to discontinue or withdraw, the investigator must show "due diligence" by documenting in the source documents steps taken to contact the subject, e.g., dates of telephone calls, registered letters, etc. A patient cannot be considered as lost to follow-up until the time point of his/her scheduled end of study visit has passed.

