5.6.6 Early study termination by the sponsor

The study can be terminated by Novartis at any time for any reason. This may include reasons related to the benefit risk assessment of participating in the study, practical reasons, or for regulatory or medical reasons (including slow enrolment). Should this be necessary, the patient

must be seen as soon as possible and treated as a prematurely withdrawn patient. The investigator may be informed of additional procedures to be followed in order to ensure that adequate consideration is given to the protection of the patient's interests. The investigator will be responsible for informing the Institutional Review Board/Independent Ethics Committee (IRBs/IECs) of the early termination of the trial.

6 Visit schedule and assessments

Patients must be seen for all visits on the designated day, or as close to it as possible. Missed or rescheduled visits should not lead to automatic discontinuation. Patients who prematurely discontinue the study for any reason should be scheduled for a visit as soon as possible, at which time all of the assessments listed for the final visit will be performed. At this final visit, all dispensed investigational product should be reconciled and the adverse event and concomitant medications reconciled on the eCRF.

EOT = End of treatment; UNS = Unscheduled visit; PSW = Premature study withdrawal

X = assessment to be recorded on clinical data base

S = assessment to be recorded on source documentation only

β -hCG = The β -subunit of human Chorionic Gonadotropin

¹ Visit structure given for internal programming purpose only.

² Prior to start of any study procedure.

³ Commencement of rescue medication with Coartem may occur after start of trial medications and up to Study Day 28 as deemed necessary by the investigator. Any patient on KAE609 who have not been rescued till Study Day 28, will be given Coartem at end of the study at Study Day 29.

⁴ A complete physical examination will be performed by the investigational staff *at screening* and include the examination of general appearance, skin, neck (including thyroid), eyes, ears, nose, throat, lungs, heart, abdomen including splenomegaly, back, lymph nodes, extremities, vascular and neurological. Body height and body weight will also be measured at screening and data recorded on clinical data base.

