9.4.3 Handling of missing values/censoring/discontinuations

No missing value of the primary variable is expected since the analysis is based on the SAF set and all patients in the SAF set should provide safety observation as they are hospitalized for the first 3 days. No missing imputation will be done in this study.

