9.4.4 Sensitivity analyses

In the past KAE609 studies, peak LFT occurred during the first 2 weeks. For patients who discontinued the study during the first 2 weeks, their peak LFT may not be observed. Analyses in [Section 9.4.2](#) will be performed by excluding those patient(s) who discontinued the study before Study Day 15 and did not experience at least 2 CTCAE grades increase from baseline in ALT or AST.

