### 5.1.4 Visit windows

When visit windows are used, all visits will be re-aligned, i.e., they will be mapped into one of the visit windows. E.g., if the Day 4 visit of a patient is delayed and occurs on Day 7, say, it will be re-aligned to visit window Day 8. In the case of major deviations from the visit schedule, or due to unscheduled visits, several assessments of a patient may fall in a particular visit window (either scheduled or unscheduled). Statistical approaches to handle multiple assessments in a given visit window are specified below.

- Of note, patients are allowed to have gaps in visits. All data collected will be displayed in listings.
- Lower limit and upper limit of the Day 15 visit is set to be Day 14 and Day 16 respectively, according to the protocol visit schedule since this is the primary analysis timepoint.
- The following rules are used to determine the window for other visits post baseline:
  - “Lower limit” = “upper limit of prior applicable visit” + 1.
  - “Upper limit” = “target day of current visit” + integer part of (“target day of next applicable visit” – “target day of current visit”)/2 with the exception of Day 29

- No upper limit for Day 29 visit
- Upper limit of Day 11 is one day before the lower limit of Day 15

For assessments that are scheduled to be performed only once on a day, [Table 5-5](#) describes the analysis windows mapping to visits (not just scheduled visits) based on study days alone. For the assessments that may be performed on multiple timepoints on a day, [Table 5-6](#) describes the analysis windows mapping to visits based on study day and time. Repeat and/or unscheduled visits (which will be numbered in the database according to new NCDS standards) will be mapped for analysis purposes in the same way. If there are multiple measurements within an analysis window, the conventions defined in [Table 5-7](#) will be used to determine the appropriate measurement to be selected for analysis.

The mapped visits will be used in the by visit analyses. However, the listings will show the collected data regardless of used in the by visit analyses.

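### The supportive analysis for unseen ALT/AST peaks removes early leavers but keeps, as non-events, patients who stayed in the study and had no test in the Day 8, 11 and 15 windows

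*SAP*

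**What the plan says.** The primary variable (SAP 2.5.1, Protocol 9.4.1) is any rise of at least two CTCAE grades in ALT or AST over the four weeks. It is analysed in the Safety set, which requires one dose and sets no minimum number or timing of tests. Nothing is imputed. SAP 2.5.3 states: "No missing value of the primary variable is expected since the analysis is based on the SAF set". Protocol 9.4.3 gives the reason: "all patients in the SAF set should provide safety observation as they are hospitalized for the first 3 days".

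SAP 2.5.4 then recognises that a peak may be missed in patients who leave in the first two weeks. It repeats the analysis "excluding those patient(s) who discontinued the study before Study Day 15 and did not experience at least 2 CTCAE grades increase from baseline". Protocol 9.4.4 has the same rule: "excluding those patient(s) who discontinued the study before Study Day 15".

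Other sections separate missed tests from leaving the study:
- Protocol section 6: "Missed or rescheduled visits should not lead to automatic discontinuation".
- SAP 5.1.4: "patients are allowed to have gaps in visits".
- Protocol 5.6.3: "Patients are considered to be withdrawn prematurely from the study if they do not complete the follow-up visits until Study Day 29".
- Protocol 5.6.5: "A patient cannot be considered as lost to follow-up until the time point of his/her scheduled end of study visit has passed".

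SAP Table 5-5 sets the chemistry windows at Days 7-9 (Day 8), 10-13 (Day 11) and 14-16 (Day 15).

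**The concern.** The supportive analysis exists to show whether unseen peaks could change the result, but its exclusion depends on disposition alone. A patient can remain in the study and still have no ALT/AST between the inpatient and Day 5 tests and Day 22 or 29. If that patient had a rise that settled in the gap, the primary proportion is too low and the supportive proportion repeats it. Agreement between the two would then be read as reassurance that it does not give. The trial aims to rule out a high incidence of abnormal liver tests, so the error runs towards calling a regimen safe. The arms have 10 or 20 patients, so one or two such patients are visible in the upper limit.

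**Working it through.** **1. One patient traced through the rules.** The patient is dosed, discharged around Study Day 4, tested on Day 5, untested on Days 7-16, and back on Day 22 or 29 below the endpoint.
- Safety set: included, because one dose was taken.
- Primary analysis: non-event, because no two-grade rise was observed and nothing is imputed.
- Supportive analysis: not excluded, because the patient did not discontinue before Day 15. Still a non-event.

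No other section removes this patient. The sampling days are inferred from the Table 5-5 chemistry column, because the Table 6-1 grid is not in the text I have.

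**2. The plan's own figures (exact binomial, Protocol 9.8.1).** They reproduce:
- P(at least 2 of 10) is 85.1% at a true rate of 30% and 3.5% at 3%. The plan states above 80% and below 5%.
- P(at least 3 of 20) is 96.5% and 2.1%. The plan states above 90% and below 5%.

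The sample-size section is not at fault.

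**3. Upper limits.** The number of uncovered patients is assumed, since the documents give none. The two-sided 95% Clopper-Pearson upper limit is 1 − 0.025^(1/n) for 0/n. Otherwise it is the 97.5% quantile of Beta(x+1, n−x).

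| Planned, both analyses | Uncovered | With uncovered non-events excluded |
|---|---|---|
| 0/10: 30.8% | 2 | 0/8: 36.9% |
| 2/20: 31.7% | 1 | 2/19: 33.1% |
| 2/20: 31.7% | 2 | 2/18: 34.7% |
| 2/20: 31.7% | 4 | 2/16: 38.3% |

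For scale, the two high incidences in Protocol 9.8 are 37.5% (3/8) and 36.4% (4/11).

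**4. Expected proportion.** Let p be the true rate, m the uncovered share and q the share of uncovered patients' events still seen on other days, with gaps unrelated to liver tests.
- Primary and stated supportive rule: p(1−m) + pmq.
- Coverage rule: [p(1−m) + pmq] / [(1−m) + pmq].

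At p = 0.30 and q = 0, with m = 0.05, 0.10 and 0.20:
- the planned rules average 28.5%, 27.0% and 24.0%;
- the coverage rule averages 30.0% in each case.

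At p = 0.30, m = 0.10 and q = 0.5:
- planned: 0.27 + 0.015 = 28.5%;
- coverage rule: 0.285 / 0.915 = 31.1%.

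So q = 0 is the extreme case, and the coverage rule can slightly overstate.

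**5. Fisher comparison (two-sided, same uncovered share in both arms).** Coartem 2/60 is assumed (3.3%, near the plan's 3%). 2/20 vs 2/60 gives p = 0.26. With 10% uncovered and excluded in each arm, 2/18 vs 2/54 also gives p = 0.26.

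**The case against.** The scenario is narrow and the plan works against it. Protocol section 6 asks that patients be seen on the designated day or as near as possible. Inclusion criteria 7 and 8 select patients likely to complete who live within reach. Protocol 5.6.2 asks for telephone contact when visits are missed, and a Table 6-1 footnote asks for laboratory tests at withdrawal. Escalation (Protocol Table 3-1) waits until the whole cohort has been followed to Day 15. Laboratory data are reviewed continuously, and the committee's outputs include ALT/AST over the first two weeks (SAP Table 2-6). The SAP sentence on gaps belongs to a mapping rule and does not relax attendance. Tests through Day 5 also fall within the stated peak period. All of this stands: it makes gaps less likely and more visible. None of it changes the supportive estimate.

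The cut-off is also a choice. No document places the peak in Days 7-16. Under the proposed rule a single Day 7 value counts as coverage, while tests on Days 6 and 17 alone do not. That stands too, so the window should be declared a convention.

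A reader might infer more than the documents support:
- **That the stated 80% detection probability is lost.** With two of ten patients unobservable, P(at least 2 events) at 30% falls from 85.1% to 74.5%. This requires that their events could be seen only in the gap, and no missed-visit rate is given. The triggers count observed patients, so the choice of supportive denominator cannot alter them.
- **That the Fisher comparison is compromised.** At 40% vs 5%, with 2 of 10 KAE609 patients and no Coartem patient uncovered, power would be 59% counting them as non-events and 70% excluding them. Nothing in the documents suggests such an imbalance.
- **That the rules fix the discontinuation of non-returners after Day 15.** Protocol 5.6.5 limits when the lost-to-follow-up label may be used. It does not set a discontinuation date, so this needs only clarification.

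**Conclusion.** The point holds as a mismatch between the supportive analysis's purpose and its exclusion rule. The effect is probably small and cannot be sized from the documents. It is zero with full attendance and grows with the number of patients untested in all three windows. It bears on the proportion and its upper limit: about 1.4 points for one uncovered patient in an arm of 20 with two events (33.1 − 31.7), and about 6 points for two in an arm of 10 with none (36.9 − 30.8). With similar gaps in both arms it does not materially affect the comparison with Coartem. The plan sets no formal hypothesis, and narratives also inform the decision. Separately, the reason for expecting no missing values is weak: inpatient monitoring is assured only to about Study Day 4, while SAP 1.1 expects peaks within 14 days. Minor-to-moderate priority; a cheap improvement.

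**What to change.** Keep the stated exclusion. Add, identically for KAE609 and Coartem and whatever the disposition status, exclusion of non-event patients with no ALT/AST value in any of the Day 8, 11 and 15 windows of SAP Table 5-5. This also settles patients who stop attending after Day 5 without a recorded discontinuation date. State that the window is an analysis convention, and report the number of uncovered patients by arm, even if it is zero. Reword SAP 2.5.3 and Protocol 9.4.3 so that they no longer rest on the three-day stay. If a worst-case row is shown, count uncovered patients as events in both arms.

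The cost is some wording and one flag from existing data, with no new collection. The supportive denominator may be slightly smaller, and the rate may be slightly overstated (31.1% against 30% in the scenario above). SAP section 4 currently records no change from the protocol analyses and would need an entry if only the SAP is altered. The SAP history shows an update after database lock, so label this post hoc if it is added after that point.

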## **2.6 Analysis of the key secondary objective**

There is no key secondary objective in this study.

## **2.7 Analysis of secondary efficacy objective(s)**

Descriptive statistics for each secondary variable will be provided by cohort and treatment group. Statistical comparison with Coartem will not be performed due to small sample size for each treatment group.

### **2.7.1 Secondary endpoints**

All efficacy analyses are secondary. Secondary efficacy variables include:

- PCR-corrected ACPR at Study Days 15 and 29;
- Uncorrected ACPR at Study Days 15 and 29;

- Proportion of patients with parasitaemia at 12, 24, and 48 hours after the first dose of study drug;
- Parasite clearance time (PCT), defined as time from the first dose until the first total and continued disappearance of asexual parasite forms which remained at least a further 48 hours;
- Fever clearance time (FCT), defined as time from the first dose until the first time the axillary body temperature decreased below and remained below 37.5°C axillary or 38.0°C oral/tympanic/rectal for at least a further 24 hours;
- Proportion of patients with ETF;
- Proportion of patients with LCF;
- Proportion of patients with LPF;
- Incidence rate of recrudescence and reinfection at Study Day 29.

Analyses of ACPRs (PCR corrected or uncorrected) will be based on the FAS and PPS. Analyses of other secondary efficacy variables will be based on the FAS.

## **2.7.2 Statistical hypothesis, model, and method of analysis**

There are no pre-specified hypotheses for secondary endpoints. Model and method of analysis are presented in the following sub-sections by topic.

### **2.7.2.1 PCR-corrected ACPR and uncorrected ACPR**

At each visit, the ACPR rate with 95% confidence intervals will be provided using the Pearson-Clopper method for each treatment group by cohort.

PCR corrected/uncorrected ACPRs at Day 29 will be summarized descriptively by the following subgroups

- Sex (male vs female)

### **Handling of missing values/censoring/discontinuations**

Data will be handled as follows:

- Patients with presence of parasitaemia which was determined to be reinfection on Day 8 or later will be counted as responders for PCR corrected ACPR and as non-responder for PCR uncorrected ACPR from the day of test
- Patients with presence of parasitaemia which cannot be determined to be recrudescence or reinfection due to missing PCR corrected/uncorrected data will be counted as non-responders from the day of test
- Patients with missing/undetermined responses at a visit due to missing blood smear data at the visit will be counted as non-responders (PCR corrected or uncorrected) unless there is a later blood smear test indicating no parasitemia
- Patients who received non rescue anti-malarial medication will be considered in the analysis as if they had not taken the anti-malarial drug.

In addition, PCR-corrected and uncorrected ACPR rate will be calculated and plotted using the Kaplan-Meier method for each treatment group by cohort in the FAS.

#### 2.7.2.1.1 Analysis of PCR-corrected ACPR using Kaplan-Meier method

For the FAS, the proportion of patients with PCR-corrected ACPR at Day 29 and 95% CI will be also estimated using the Kaplan-Meier method ([Stepniewska and White 2006](#) and [WHO 2015](#))

**Event** = PCR-corrected non-responder during the study (same as at Day 29, See Section 2.1). The event time is the first time when the patient becomes a non-responder based on PCR-correction. If a patient parasite is not cleared at all, Day 7 is considered as the event time.

The PCR-corrected responder rate at Day 29 is estimated by the survivor function at Day 29 using the Kaplan-Meier method.

##### **Rule for censoring:**

The following censoring rules will be applied to the patients who were not non-responder

- Patients who had a new infection (i.e., reinfection) with *P. falciparum* or other species without *P. falciparum* recrudescence on or after Day 8 will be censored at the time of the first PCR that indicate the infection;
- Patients who received non-rescue antimalaria medication for other infections, such as *P. falciparum* gametocytes, will be censored at the first time of antimalaria medication;
- Patients who have parasites at Day 8 or later but cannot be determined as recrudescence or new infection due to missing PCR genotyping will be censored at the time of the first malaria blood film with presence of parasitaemia on or after Day 8.
- other patients not classified as non-responder will be censored at the time of last parasitemia assessment.

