9.5.1.1 PCR-corrected ACPR and uncorrected ACPR

At each visit, the ACPR rate with 95% confidence intervals will be provided using the Pearson-Clopper method for each treatment group by cohort.

Data will be handled as follows:

- Treatment failures after 7 days (i.e., Study Day 8) due to reinfection based on PCR genotyping are not considered as failure for PCR-corrected analyses.
- For parasitological uncorrected ACPR, patients will be treated as failure on and after the visit when a new infection (i.e., reinfection) with *P. falciparum* or other species is detected.
- Patients who received rescue medication for the treatment of *P. falciparum* malaria (except for the treatment of a new infection) will be considered treatment failures. Patients who received other concomitant medication having an effect on malaria for reasons other than rescue therapy e.g., for the treatment of *P. vivax* (e.g., primaquine, certain antibiotics (sulfonamides, tetracycline, etc.)) will be considered in the analysis as if they had not taken the drug.
- Patients will be counted as failure at a visit (e.g., Study Day 15, etc.) if (a) they did not have a parasite count i.e., missing parasite count at that visit unless these patients could be classified as cured based on absence of parasitaemia (parasite count = 0) at a later time (e.g., Study Day 29), or (b) they did not have valid PCR evaluations at baseline and the visit if parasitaemia was present at that time (e.g., Study Day 15).

In addition, PCR-corrected ACPR rate will be calculated and plotted using the Kaplan-Meier method ([Stepniewska and White 2006](#); [WHO 2016](#)) for each treatment group by cohort in the FAS. Treatment failure is the event for analysis and patients without Study Day 29 data and treatment failure is considered as censored instead of treatment failure. The PCR-corrected ACPR rate at Study Day 29 is estimated by the survival function at Study Day 29. Patients who had a new infection (i.e., reinfection) with *P. falciparum* or other species without *P. falciparum* recrudescence on or after Study Day 8 will be censored at the time of the first PCR that indicate the infection; patients who took antimalarial medications for reinfection or reasons other than

rescue medication given for *P. falciparum* related treatment failure will be censored at the first time of such antimalarial medications; other patients without treatment failure will be censored at the time of last parasitaemia assessment.

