### **PCR-corrected ACPR at Day X where X=15 and 29**

- A patient is considered as non-responder at Day X if the patient experiences an ETF, LCF, or LPF from Day 5 to Day 7.
- A patient is also considered as non-responder if the parasitaemia is not cleared by Day X unless the patient discontinues the study prior to Day X without ETF, LCF, or LPF, in which case the response is considered as missing,
- A patient is considered as non-responder at Day X if the patient has a parasite recrudescence from Day 8 to Day X
- A patient is considered as responder (corrected ACPR) at Day X if the patient is not classified as a non-responder by Day 7 and has a new infection from Day 8 to Day X based on PCR genotyping unless that the patient did not have parasites cleared prior to the new infection, in which case the patient is considered as non-responder.
- A patient is considered as responder at Day X if the patient is not classified as a non-responder at Day X and the patient has a malaria blood film showing absence of parasitaemia at Day X or later if Day X is missing.
- The response for a patient is considered as missing/undetermined if
  - The patient has parasitaemia present from Day 8 to Day X for which the PCR genotyping of recrudescence or new infection is not determined.
  - The patient is not classified as a non-responder at Day X and the malaria blood film result at Day X is missing and not followed by a subsequent negative result.

Note - The outcome of PCR-corrected ACPR and uncorrected ACPR at a given day is categorized as responder or non-responder to distinguish from failure used in early treatment failure, late clinical failure or late parasitological failure. With this notation, ACPR rate is the proportion of responders.

A patient with presence of parasitaemia at more than 7 days after the first dose is considered as non-responder for uncorrected ACPR. We reclassify such a patient as responder for PCR-corrected ACPR if presence of parasitaemia at more than 7 days after the first dose is due to new infection. Whether the presence of parasitaemia after 7 days is due to recrudescence or new infection is determined and provided by the central laboratory.

The above definitions of ACPRs are purely based on the malaria blood film and PCR results without consideration for taking concomitant anti-malaria drugs. In statistical analyses, some

responses may be overridden for patients who take concomitant anti-malaria drugs (see [Sections 2.5 and 2.7](#)).

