##### **Rule for censoring:**

The following censoring rules will be applied to the patients who were not non-responders

- Patients who received non-rescue anti-malaria medication will be censored at the first time of anti-malaria medication;
- other patients will be censored at the time of last parasitemia assessment.

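### In the supplementary Kaplan-Meier ACPR analyses, censoring at non-rescue antimalarial use depends on the patient's later outcome, which can only lower the Day 29 cure estimate

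*SAP*

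**What the plan says.** SAP 2.7.2.1.1 defines the Kaplan-Meier event as "PCR-corrected non-responder during the study (same as at Day 29, See Section 2.1"), so event status is settled by the whole follow-up. The censoring rules then open with "The following censoring rules will be applied to the patients who were not non-responder". Under that lead-in, "Patients who received non-rescue antimalaria medication for other infections" are censored at the first such medication.

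SAP 2.7.2.1.2 (uncorrected ACPR) repeats the lead-in, "The following censoring rules will be applied to the patients who were not non-responders", and adds: "Patients who received non-rescue anti-malaria medication will be censored at the first time of anti-malaria medication". This version has no limit on the reason for use.

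Responder status itself takes no account of these drugs. SAP 2.1.1.1 says: "The above definitions of ACPRs are purely based on the malaria blood film and PCR results without consideration for taking concomitant anti-malaria drugs". It allows responses to be overridden under 2.5 and 2.7, but neither section has a rule that removes a failure occurring after such a drug. For the proportion analysis, SAP 2.7.2.1 treats users as if they had not taken the drug.

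Protocol 9.5.1.1 censors "patients who took antimalarial medications for reinfection or reasons other than" rescue for *P. falciparum* treatment failure at the first such medication. It specifies Kaplan-Meier only for PCR-corrected ACPR. SAP Section 4 lists no change to the protocol analyses.

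**The concern.** Take two patients given a non-rescue antimalarial on Day 10. One recrudesces on Day 22 and the other stays clear to Day 29. Under the SAP the first stays at risk to Day 22 and is an event; the second is removed on Day 10. On Day 10 nothing distinguishes them, so the censoring is decided by what happens later. Kaplan-Meier requires that censoring at a given time not depend on the future outcome.

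The rule also answers neither of the two coherent questions. Censoring every user estimates cure without the other drug's influence. Ignoring the drug estimates cure whatever else was taken. The SAP ignores the drug for failures and censors for cures.

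Separately, the two curves use different reason lists. A patient who stays clear and took a non-rescue antimalarial for something other than another infection is censored in the uncorrected curve. In the PCR-corrected curve the same patient is kept as cured to the last assessment.

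**Working it through.** The documents give no Kaplan-Meier cure rate and no expected rate of non-rescue antimalarial use, so there is no planned figure to reproduce. All counts, cure rates and user shares below are assumptions. The arm sizes of 10 and 20 come from Protocol 3.1 and SAP 1.1.

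**Three rules on the same data**
- A (SAP): every failure by Day 29 is an event; only patients who never fail are censored at drug use.
- B (censor all): every patient is censored at first drug use unless failure has occurred by then.
- C (ignore the drug): simple proportion cured.

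The estimate is S(29) = product over failure days of (1 − events / number at risk). In the worked arms, all drug use is on Day 10 and all failures are on Day 22, so there is one factor.

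| Arm | Failures, no drug | Users who fail | Users cured | A | B | C |
|---|---|---|---|---|---|---|
| 10 | 2 | 1 | 1 | 6/9 = 66.7% | 6/8 = 75.0% | 7/10 = 70.0% |
| 20 | 2 | 1 | 1 | 16/19 = 84.2% | 16/18 = 88.9% | 17/20 = 85.0% |
| 20 | 3 | 1 | 4 | 12/16 = 75.0% | 12/15 = 80.0% | 16/20 = 80.0% |
| 20 | 2 | 2 | 2 | 14/18 = 77.8% | 14/16 = 87.5% | 16/20 = 80.0% |
| 20 | 2 | 0 | 2 | 16/18 = 88.9% | 16/18 = 88.9% | 18/20 = 90.0% |

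In the first three rows one failure follows the drug, and A lies 8.3, 4.7 and 5.0 points below B. In the last row none does, and A equals B. The remaining gap to C there is that of ordinary censoring.

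**Direction**
- Against C: the events are the same and the number at risk is never larger, so no factor can be larger.
- Against B: a user who fails later is an event instead of a censored patient whose weight would be shared among those still at risk, some of them cured.
- In 20,000 random small data sets, A was never above B and never above C.

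**Large-sample size**

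This used 400,000 simulated patients per setting, a constant failure hazard from Day 5 to Day 29, failures detected at the visit days, and drug use uniform over Days 5 to 28. Use was independent of prognosis and the drug had no effect. Day 29 cure under rule A:

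| True cure | 5% users | 10% | 20% | 30% |
|---|---|---|---|---|
| 90% | 89.7% | 89.4% | 88.6% | 87.7% |
| 80% | 79.6% | 78.9% | 77.7% | 76.0% |
| 60% | 59.0% | 58.1% | 56.3% | 54.1% |

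Rule B returns the true rate within about 0.2 points. At 80% cure and 5% users the shortfall is 80.0 − 79.6 = 0.4 points against the true rate, or about 0.5 against B in the same simulated data (80.1%).

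An effective drug shrinks the gap. At 80% cure without the drug and 20% users, A against B is 78.6% against 80.0% if the drug halves later failure. It is 79.6% against 80.1% if the drug prevents all later failure; the rest comes from failures that preceded the drug but were detected after it.

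**Frequency**

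In an arm of 20 with 5% users and 20% failure, the expected number of users who also fail is 20 × 0.05 × 0.20 = 0.2, and only some of those fail after the drug.

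**The case against.** The strongest reply is that this is a supplementary, descriptive output and the triggering event should be rare. Both points stand. Kaplan-Meier is added to the exact-interval ACPR proportions, which ignore these drugs for failures and cures alike. Other antimalarials are prohibited (Protocol 5.5.8) and treated as protocol deviations (SAP 2.4.2). Treatment given after a failure does no harm, because that patient is rightly an event already.

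Four stronger readings are tempting, and the documents do not support them.
- *Efficacy results, or the dose comparison, are materially biased.* Only the Kaplan-Meier ACPR estimates are touched. Secondary variables are not statistically compared with Coartem (Protocol 9.5, SAP 2.7), and nothing in the documents supports a high user share.
- *The SAP plainly contradicts the protocol on who is censored.* The antimalarial clause in Protocol 9.5.1.1 carries no such condition. However, its closing clause on remaining patients without treatment failure can be read as implying that the groups before it had not failed either. For uncorrected ACPR there is no protocol Kaplan-Meier rule to depart from.
- *The narrower reason list biases corrected cure upward.* If the drug has no effect, keeping users of the omitted kind at risk, cured and failing alike, simply ignores the drug and creates no bias. An upward bias needs an effective drug. What stands is the inconsistency between the two curves.
- *Censoring every user is the only valid choice.* Ignoring the drug is equally consistent and agrees with the proportion analysis. In the row with two failing users, B (87.5%) lies further from C (80.0%) than A does (77.8%).

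Rarity does not make the rule valid. The SAP itself foresees treatment for gametocytes, and Protocol 9.5.1.1 foresees drugs for *P. vivax* and certain antibiotics. Some Coartem use is also hard to classify: Protocol 5.5.4 calls it rescue after a second vomited KAE609 dose, whereas SAP 2.4.2 ties rescue to treatment failure.

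**Conclusion.** The concern holds in a limited form. As written, both Kaplan-Meier sections censor according to later outcome, which is not valid and matches neither consistent handling of these drugs. The error has one direction: Day 29 Kaplan-Meier cure can be understated, never overstated, relative to censoring all users or ignoring the drug.

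Whether it occurs depends on at least one failure following such a drug; with none, the SAP rule is ordinary censoring. The average loss is small at low use, but a single such failure moved the estimate by about 5 to 8 points against censoring all users in the worked arms of 10 and 20. The mismatch in reasons between the two curves follows from the text alone and needs no assumption about rates.

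**What to change.** In SAP 2.7.2.1.1 and 2.7.2.1.2, drop the restriction to patients who never become non-responders from the antimalarial rule. A possible wording for both: *For every patient, whatever the later outcome, time runs to the earlier of first non-response and first antimalarial taken for any reason other than rescue for P. falciparum treatment failure. Non-response on or before that date is an event; otherwise the patient is censored on that date.* This puts the Protocol 9.5.1.1 reasons in both sections.

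Add a sensitivity analysis that ignores the drug for all patients, in line with SAP 2.7.2.1, and record the choice in SAP Section 4.

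The cost is a few sentences, one derivation change and one extra run, with no new data. The document history shows that the SAP's latest update came after database lock, so a change now should be labelled as post-lock. The downside is that a failure seen after such a drug is no longer an event in the main Kaplan-Meier curve. It still counts in the exact-interval proportion and in the sensitivity analysis.
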